10 SUPPORTING DOCUMENTATION AND OPERATIONAL CONSIDERATIONS

10.1 Regulatory, Ethical, and Study Oversight Considerations

10.1.1 *Informed Consent Process and HIPAA Authorization*

10.1.1.1 *Consent/Accent and Other Informational Documents Provided To Participants*

Consent forms describing in detail the injections, study procedures, and risks are given to the participant and written documentation of informed consent is required prior to starting intervention. The following consent materials are submitted with this protocol:

- XRBUP vs XRNTX Consent form.
- Informed consent quiz
- HIPAA Authorization form

10.1.1.2 *Consent Procedures and Documentation*

Informed Consent:

Study procedures will be described in detail to the subjects by a trained study staff member during the informed consent session.. The consent form and session will include detailed information about the study medication; that is, a description of the medication, rationale for why it is being studied, frequency of dosing and length of treatment, potential side effects, safeguards and emergency procedures. Information will also be provided about the psychosocial treatment, frequency of visits and length of treatment, safeguards and emergency procedures, etc. Collection of lab specimens (number of venipunctures and urine specimens required) will be reviewed. Eligibility will be reviewed. The number and frequency of the research interviews and self-assessments will be reviewed

In addition, subjects will be assured that their participation is voluntary and that withdrawal from the study does not jeopardize current or future treatment. Patients will also be told that if at any time during the study the research team and the clinical treatment team feel that the patient needs more intensive, standard treatment, the patient will be referred to one of the available inpatient treatment programs in Philadelphia. All subjects will be informed of potential risks and benefits involved in the study. Potential medication side effects will be described to all subjects. Patients will be informed that their participation in the treatment trial may be discontinued at any time because of serious medication side effects, their noncompliance with treatment, missing appointments or if continued participation is considered an endangerment to their welfare.

Informed Consent quiz:

At the end of the consent session, a quiz is given. Subjects scoring below 100% correct will receive additional instruction regarding the study and consent form. Incorrect questions from the quiz will be administered again until all questions are answered correctly. All participants are provided with a hard copy of the consent form that includes the name and telephone numbers of the investigative team, and the Chair of Penn's Institutional Review Board (IRB). A 24-hour Emergency contact is provided in case of an adverse consequence or any other emergency.

HIPAA Authorization Form:

After signing the consent, participants would also be asked to grant access to their medical records at University of Pennsylvania and other institutions to share their health information that may include diagnoses, medications, hospital admissions, laboratory and imaging studies and participation in treatment programs including substance use disorder. This will be done by signing a **"RESEARCH PARTICIPANT AUTHORIZATION TO OBTAIN AND REVIEW HIPAA-PROTECTED MEDICAL RECORDS AND COMMUNICATION WITH THEIR HEALTH CARE PROVIDERS"**.

Intake Procedures at Treatment Facilities:

Participants found to be eligible at screening who are unable to attend intake at our center because they are currently inpatient, will undergo intake procedures at their inpatient treatment facility. Private space for the intake sessions will be secured in coordination with inpatient clinical staff.

The following procedures will be done at the inpatient facilities to reduce the delay in enrolling eligible participants.

- Informed consent, informed consent quiz and HIPAA authorization form administered by the trained study member.
- Non-invasive assessments and measures will be administered by the trained study members using portable tablets.

10.1.2 Study Discontinuation and Closure

The study may be discontinued at any time by the IRB, the Sponsor, the FDA, or other government agencies as part of their duties to ensure that research subjects are protected.

10.1.3 Confidentiality and Privacy

Information about study subjects will be kept confidential and managed according to the requirements of the Health Insurance Portability and Accountability Act of 1996 (HIPAA). Those regulations require a signed subject authorization informing the subject of the following:

- What protected health information (PHI) will be collected from subjects in this study
- Who will have access to that information and why

- Who will use or disclose that information
- The rights of a research subject to revoke their authorization for use of their PHI.

In the event that a subject revokes authorization to collect or use PHI, the investigator, by regulation, retains the ability to use all information collected prior to the revocation of subject authorization. For subjects that have revoked authorization to collect or use PHI, attempts should be made to obtain permission to collect at least vital status (i.e. that the subject is alive) at the end of their scheduled study period.

10.1.4 Safety Oversight

DATA AND SAFETY MONITORING:

10.1.5 *During the course of the study, data and safety monitoring will be performed on an ongoing basis by the Principal Investigator- [name], Medical Director & Regulatory Sponsor- [name], Study Physician- [name], research staff, and the site IRB. The PI [name] PhD will have overall responsibility for data analysis and management, as well as overall responsibility for safety and data monitoring on a day-to-day basis. The PI will be responsible for reporting the adverse events and serious adverse events. This study will be monitored according to the monitoring plan as noted in DSMP. The study physician will be available to review medical issues related to participation for each participant on an ongoing basis as outlined in this protocol. The internal monitoring will be conducted on site at Center for Studies of Addiction by the study coordinator appointed by the PI. The study coordinator is qualified by education, experienced and have completed training on GCP. See their certifications and qualifications in the e-regulatory binder for the study. The study coordinator will be responsible for collecting and recording all clinical data. This includes ensuring that all source documents exist for the data on the case report forms, ensuring all fields are completed appropriately, and all corrections are done according to GCP. Any inconsistencies/deviations will be documented. The study coordinator will perform regular chart reviews to verify data integrity. Quality Assurance and Quality Control*

This study will be monitored according to the monitoring plan as noted above. The investigator will allocate adequate time for such monitoring activities. The Principal Investigator will also ensure that the monitor or other compliance or quality assurance reviewer is given access to all the above noted study-related documents and study related facilities (e.g. pharmacy, diagnostic laboratory, etc.), and has adequate space to conduct the monitoring visit.

10.1.6 Data Handling and Record Keeping

Subject Confidentiality

This study will utilize directly identifiable protected health information (PHI). PHI, as defined by HIPAA, means individually identifiable health information about an individual that is transmitted or maintained by electronic media or in any other form or medium. PHI includes demographic information that is created or received by a health care provider, health plan, employer, or health clearinghouse. PHI relates to the past, present, or future physical or mental health or condition of an individual; the provisions of health care to an individual; or the past, present, or future payment for the provision of health care to an individual; and identifies the individual or can reasonably be used as a basis to identify an individual. The following PHI will be collected for this study:

- Name
- Postal address information
- All elements of dates, such as birthdate and date of visit, (except year) for dates directly related to an individual and all ages over 89)
- Telephone and fax number
- Electronic mail addresses
- Social security numbers (*for study compensation*)
- Medical record numbers (*for ordering MRIs, medications,*
- *Access to medical records to determine eligibility and safety for participation*

In accordance to University of Pennsylvania's policy regarding how PHI is handled, managed, and disseminated, study personnel will utilize an institutionally secured and managed network drive.

Institutionally secured and managed network drive: The CSA/TRC utilizes a departmental shared drive to securely store PHI. The CSA/TRC shared drive is managed and secured by The Penn Medicine Academic Computing Services (PMACS). Access to the shared drive requires password access to a departmental device (CSA/TRC desktop or laptop) then additional password access to the departmental shared drive. After being granted access to the shared drive, one must have an encryption code to access the files storing PHI. Therefore, the only CSA/TRC employees that will have access to the PHI connected to this study will be the approved study personnel (Principal Investigator, Project Supervisor, Clinical Research Coordinators).

Any paperwork that includes PHI (such as SSN on subject compensation forms) will be kept in a locked draw within a locked office. To reduce the possibility of breaches in subject confidentiality, subjects will be given a unique identifier to place on their demographic information, questionnaires, behavioral ratings, and data from scan sessions. Only the study personnel will have access to the code. Five years after completion of the study, the subject code will be destroyed. Data will be destroyed 8 years after study completion.

Subject Privacy

The study personnel will maintain a high level of privacy for this research study. To respect those boundaries, several safeguards will be in place. Subjects will be screened and interviewed in a private office at the CSA/TRC offices located at [name] or at participant's treatment facilities. When contacting subjects, information about mental and physical health will not be

disclosed; telephone messages or voicemails will be worded so as to not reveal the subjects study status, diagnoses, or any other confidential information.

10.1.7 Protocol Deviations

Exception

A one-time, intentional action or process that departs from the IRB-approved study protocol, intended for one occurrence. If the action disrupts the study progress, such that the study design or outcome (endpoints) may be compromised, or the action compromises the safety and welfare of study subjects, advance documented approval from the Regulatory Sponsor, IRB, and other local regulatory review committees per institutional guidelines is required. Approval from the Regulatory Sponsor must be received prior to submission to the IRB and local regulatory review committees for approval.

Deviation

A one time, unintentional action or process that departs from the IRB-approved study protocol, involving one incident and identified retrospectively, after the event occurred. If the impact on the protocol disrupts the study design, may affect the outcome (endpoints) or compromises the safety and welfare of the subjects, the deviation must be reported to the Regulatory Sponsor within 10 business days of PI knowledge, and to local regulatory review committees per institutional guidelines. Acknowledgement from the Regulatory Sponsor must be received prior to submission to local regulatory review committees.

Other deviations should be appropriately documented (such as a subject missing a visit unless a critical/important treatment or procedure was missed and must have been done at that specific time) per site policies/procedures.

We will include the following information on the Sponsor-supplied exception/Deviation form: protocol number, subject study number, comprehensive description of the exception/Deviation from the protocol, rationale and corrective and preventative action plan (deviations only). All completed exception/Deviation forms will be signed by the Principal Investigator (or physician sub-investigator) and submitted to the Sponsor Project Manager for review.

Once approval of the exception request or acknowledgement of the deviation has been granted by the Regulatory Sponsor, the exception or deviation will be submitted to all applicable committees for review and approval.

10.1.8 Publication and Data Sharing Policy

Neither the complete nor any part of the results of the study carried out under this protocol, nor any of the information provided by the sponsor for the purposes of performing the study, will be published or passed on to any third party without the consent of the study sponsor. Any investigator involved with this study is obligated to provide the sponsor with complete test results and all data derived from the study.

10.1.9 Conflict of Interest Policy

Any investigator who has a conflict of interest with this study (patent ownership, royalties, or financial gain greater than the minimum allowable by their institution, etc.) must have the conflict reviewed by a properly constituted Conflict of Interest Committee with a Committee-sanctioned conflict management plan that has been reviewed and approved by the study sponsor prior to participation in this study. All University of Pennsylvania investigators will follow the University conflict of interest policy.

10.2 LIMITATIONS

LIMITATIONS AND ALTERNATIVE RESULTS: We have carefully considered **potential limitations of our study and alternate designs**. Several domains that may be of interest are not included (e.g., Affect Regulation) because task selection is based on a conceptual model and to optimize subject burden. In our past experience, scanning participants for > 1-hour results in substantial movement artifact that can bias imaging results. Regarding affect regulation, we are including a well-validated self-report measure and other psychological measures as baseline predictors/covariates in the analysis. We have focused on a model-driven analysis. However, this sample may allow a data-driven, model-free approach. This limitation can be addressed by exploratory analyses using advanced methods (e.g. machine learning). Although our proposed sample size provides ample power to test our primary hypotheses and model building, validation will likely require an independent sample rather than resampling techniques for cross validation.

Strengths of Proposed Research: To our knowledge, this would be the first investigation of the use of = BOLD fMRI signal during cognitive tasks and connectivity to characterize treatment outcomes for two extended release MAT medications. The study is carefully designed and powered to evaluate the outcomes of interest. The use of larger sample sizes than previous research and novel medication will provide the strongest possible test of our hypotheses. We have demonstrated the feasibility of recruitment to studies with similar requirements, have identified brain regions of interest through our prior research, and have performed extensive pilot-testing of all paradigms. The significance of this project is its potential to advance theory and treatment by elucidating brain-behavior mechanisms.

13 APPENDIX

13.1 Schedule of Activities (SoA)

	Screening detox and randomization (Day -14)	MRI Scan 1 Baseline (day 0)	Induction to XRBUP or XRNTX (day 0-10)	Injection 1 (day 10) + weekly follow up	Injection 2 (day 40)	MRI Scan 2 On Treatment (day 55)	Injection 3 (Day 70)	Weekly Follow- up End of study and referral (Day 100)
Psychiatric and medical								
Demographics (age ¹ , sex ¹ , edu ¹)		X						
History, physical and labs (C.4.a)		X						
SILS		X						
MINI (EOS* – end of study)		X						X EOS*
Addiction Severity Index ¹		X						X EOS*
Clinical/Behavioral (C.3.a)								
HAM-D ² , HAM-A ² , COWS ²	X	X	X		X	X		X
SOWS, Opioid Craving Scale ² , SF-MPQ-2 ² , STAI-6		X	X	X	X	X		X
TLFB interview	X	X	X		X	X		X
Ten-drug urine drug screen (UDS)	X	X	X	X	X	X		X
Go-NoGo errors of commission ²		X		X				
Neuroimaging (Section C.3.b)								
Go-NoGo fMRI ³		X			X			
Opioid Cue task fMRI ³		X			X			
Resting-state fMRI ³		X			X			
MPRAGE (anatomical MRI scan)		X			X			

PRINCIPAL INVESTIGATOR SIGNATURE

STUDY SPONSOR: [name]

STUDY TITLE: **Open label comparison of injectable extended release preparations of buprenorphine (Brixadi®) and naltrexone (Vivitrol®) for the treatment of opioid use disorder**

STUDY ID 843403

PROTOCOL VERSION V5.0

I have read the referenced protocol. I agree to conduct the study in accordance to this protocol, in compliance with the Declaration of Helsinki, Good Clinical Practices (GCP), and all applicable regulatory requirements and guidelines.

Principal Investigator Name	[name]	Signature
Affiliation:	University of Pennsylvania	Date 7/17/2023

END OF DOCUMENT

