2 INTRODUCTION AND RATIONALE

This document is a protocol for a human research study. This study is to be conducted according to US and international standards of Good Clinical Practice (FDA Title 21 part 312 and International Conference on Harmonization guidelines), applicable government regulations and Institutional research policies and procedures. This proposal brings four main innovations: It would be the first neural systems' level investigation of the cognitive effects of extended-release preparations of a partial opioid agonist (XRBUP) and an antagonist (XRNTX). These formulations remove the pharmacokinetic and motivational imbalance between the monthly injectable naltrexone and daily sublingual buprenorphine that were compared in prior research (Wang et al 2015). In addition to differences in pharmacokinetics, long acting formulations are likely to have a different effect on patients' expectations of possible reward, which directly impacts dopaminergic signaling that regulates salience of drug and non-drug stimuli. Second, it would be one of the first comprehensive investigations of the cognitive effects of buprenorphine in OUD. Third, it would apply machine-learning algorithms to the integrated brain-behavior models to explain the individual heterogeneity of treatment response to MAT. Last, this would be the 1st study of the next generation injectable buprenorphine (Brixadi) that is expected to appear on the US market by September 2023 but is already approved by the FDA in terms of safety and efficacy. The significance of this project is in its potential to advance OUD theory and treatment by elucidating the brain mechanisms of vulnerability to relapse. Further, the results of this study could lay the foundation for improving treatment outcomes in OUD and in SUD in general. Project goals also directly address national public health priorities recently outlined by the directors of NIDA and the NIH: finding novel and increasing the effectiveness of available OUD treatment strategies (Volkow et al 2017).

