The clinical management of XRBUP is similar to XRNTX except that induction to XRBUP requires partial detoxification followed a weekly dose of injectable XRBUP, while induction on XRNTX requires complete abstinence (Lofwall et al 2018). The goal of the detoxification and induction phase of the experiment is to establish a uniform starting point for both monthly formulations. To achieve it, we will detoxify all participants to abstinence and randomize after abstinence from illicit opioids has been achieved. Outpatient detoxification to abstinence takes between 5 and 10 days. Following detoxification, the XRBUP participants will receive a combination of 8mg, 16mg, and 24mg strengths of weekly XRBUP, not to exceed 32 mg/week, followed by the injection of 64mg, 96mg, or 128mg of monthly XRBUP. If clinically indicated, supplemental doses of sublingual buropenorphine/naloxone (Suboxone) may be used. If clinically indicated, the induction procedure may be extended by up to one week, using the same approach. The total duration of induction to Brixadi will not exceed 14 days. The XRNTX participants will receive 50 mg of oral naltrexone for 7-10 days after detoxification followed by the 1st XRNTX (380 mg naltrexone IM) injection. The use of symptom-driven titration of weekly XRBUP during induction reflects current best practices in administration of the drug and increases participant safety and comfort. The XRBUP induction period is also intended to synchronize the timepoint at which both cohorts begin their monthly treatments. The non-opioid detoxification will follow the procedure described in our previous neuroimaging studies (Langleben et al 2014, Langleben 2015, Wang et al 2018). Participants who are opioid-positive upon screening will undergo office-based withdrawal management (detox) by the study physicians using FDA-approved generic medications to alleviate opioid withdrawal symptoms following a symptom-triggered approach that includes clonidine 0.1 mg tid, dicyclomine 20 mg qid, clonazepam 0.5 mg q12 hrs PRN, diphenhydramine 25 mg PRN, non-steroidal anti-inflammatory medicines PRN, Trazodone 50 mg qhs and oral hydration solutions (Molenberghs et al 2005). The induction to XRNTX or XRBUP will commence immediately after the baseline MRI session. The 1st monthly injection will be administered by an experienced nurse practitioner after induction is completed (approximately 7-14 days later).

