Neuroimaging (MRI): The MRI session will take place after detoxification and immediately before MAT induction (Table 1, Figure 1). This baseline time-point has been used successfully in our prior studies (Langleben et al 2014, Wang et al 2015) Participants will be escorted to the MRI facility where the investigator will meet them, review the consent and MRI screening form, and answer any remaining questions. Participants will be placed in the scanner in a supine position. The stimuli are rear projected to the center of the visual field using a PowerLite 7300 Video projector system (Epson America, Inc.) and viewed through a mirror mounted on the head coil. Participants will be given a non-ferromagnetic scroll wheel (FORP™, Current Design Inc., Philadelphia, PA) to respond during the tasks. Neuroradiologists will review the scans for clinically significant abnormalities. fMRI data will be acquired during (a) MPRAGE T1 image acquisition (5 min), (b) resting-state fMRI (5 min), (c) Go-NoGo task (5.5 min), (d) visual opioid cue task (10.5 min). The Go-NoGo and the visual opioid cue task will be counterbalance between scan 1 and 2. The total time in the scanner, including time for positioning removal and structural imaging, will not exceed 60 minutes.

STUDY MEASURES: will be administered by the study coordinator or psychologist with appropriate level of clinical training and certification (MA, PsyD or PhD):

Demographic and Clinical (Appendix Section 12.1): We use PhenX protocols (phenxtoolkit.org).

Demographical Information: Standard demographical information will be collected during phone screening and baseline study appointments, such as height, weight, preliminary fMRI eligibility, contact information, years of education etc.

MINI International Neuropsychiatric Interview (MINI) (Sheehan DV, 1998; 59(suppl 20)). The MINI is a clinician administered neuropsychiatric interview for symptoms across 17 of the most common mental health disorders. The DSM-5 version of the MINI will be administered.

Addiction Severity Scale Lite (ASI-Lite) (McLellan, 1997) The Addiction Severity Scale Lite is a shortened version of the full clinical interview. The measure collects information on demographics, employment, legal status, alcohol/drugs, family/social relationships, and psychiatric status. This measure is administered by a clinician.

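### The schedule puts randomisation ahead of the baseline scan, and nothing in the plan withholds the arm until that scan is done

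*Combined protocol and SAP*

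**What the plan says.** Four places in the protocol bear on the order of events.

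- **Section 13.1, Schedule of Activities.** The first column is headed "Screening detox and randomization (Day -14" and the next "MRI Scan 1 Baseline (day 0".
- **Section 6.1, withdrawal management and induction.** The plan is that "we will detoxify all participants to abstinence and randomize after abstinence from illicit opioids has been achieved". On duration it says: "Outpatient detoxification to abstinence takes between 5 and 10 days". On what follows the scan: "The induction to XRNTX or XRBUP will commence immediately after the baseline MRI session".
- **Section 6.1, neuroimaging.** "The MRI session will take place after detoxification and immediately before MAT induction".
- **Section 6.3, randomisation and blinding.** Urn randomisation is stratified by sex on the randomisation day, but that day is not placed before or after Scan 1.

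On masking, the title and Sections 3.1 and 4.2 call the trial open label. Section 4.1 calls it single-blind without naming the blinded party, and Section 6.3 describes how a blind would be broken.

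The primary test is the Session (PRE, ON) by Group interaction (Sections 1.1 and 9.1). Section 9.3 defines one analysis population: randomised participants who received at least one dose of study drug. Section 7.2 allows replacement of people who are randomised but not injected.

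**The concern.** A baseline is protected from treatment assignment only if it is measured before the participant knows the assignment. The schedule is the only part of the plan that orders randomisation against Scan 1, and it puts randomisation first. If the arm is then disclosed, anything the participant expects from an agonist or an antagonist can affect the PRE scan. The primary contrast subtracts PRE from ON, so PRE carries as much weight as ON. The PRE-to-ON change scores are also predictors in the treatment-outcome models of Section 9.1.

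The protocol considers expectation relevant to this signal. Section 2 says that expectations of possible reward are something "which directly impacts dopaminergic signaling that regulates salience of drug and non-drug stimuli", and the opioid cue task measures the response to such stimuli.

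The second stake is selection. Someone who learns the arm, dislikes it and leaves before the first dose falls outside the all-treated population and may be replaced. If that happens more in one arm, the groups analysed are no longer the groups randomised.

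**Working it through.** The plan gives no figure on this point, so the check is mainly one of sequence.

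**1. Order of events**

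| Source | Randomisation | Scan 1 | Induction |
|---|---|---|---|
| 13.1 | Column labelled Day -14, with screening and detoxification | Next column, day 0 | Third column, days 0-10 |
| 6.1, withdrawal management | After abstinence | Before induction | Immediately after the scan |
| 6.1, neuroimaging | Not placed | After detoxification, before induction | After the scan |
| 6.3 | Day not placed against the scan | Not mentioned | Not mentioned |

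Induction differs by arm and starts straight after the scan, so the allocation must exist by then. Abstinence fixes the earliest time for randomisation and induction fixes the latest. Scan 1 lies between the two, and only the schedule says which side randomisation falls on: before.

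**2. Room for a gap.** Assume detoxification starts on Day -14. With 5 to 10 days needed, abstinence is reached between Day -9 (-14 + 5) and Day -4 (-14 + 10). That leaves 4 to 9 days before a day 0 scan in which Section 6.1 would permit randomisation. If detoxification starts later, the gap may be close to zero.

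**3. What a shift at PRE does.** The interaction is

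D = (ON − PRE in XRNTX) − (ON − PRE in XRBUP).

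Let e(PRE) and e(ON) be the differences between arms that come only from knowing the arm. If the target is the drug effect alone,

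bias in D = e(ON) − e(PRE).

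- Shift at PRE only: the bias equals that shift in size.
- Fraction r of the shift still present at ON: the bias is (1 − r) times the shift, and zero at r = 1.
- Arm disclosed after PRE: e(PRE) = 0 and the bias is e(ON).

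If the target is instead the effect of assignment to an open-label treatment, e(ON) belongs to the effect and the bias is the whole of e(PRE).

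**4. Scale, on assumed shifts.** The documents give no shift, so these values are assumptions. Inputs: 80 per group and d = 0.42 (Section 9.2), one-sided test, alpha 0.05 (assumed, because it is not stated for this test). With net bias b in change-score SD, type I error = 1 − Φ(1.645 − b√(80/2)) if b lies in the hypothesised direction, and power = Φ((0.42 − b)√(80/2) − 1.645) if it opposes it.

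| Net bias b | b / 0.42 | Type I error, bias in favour | Power, bias against |
|---|---|---|---|
| 0 | 0% | 5.0% | 84.4% |
| 0.05 | 12% | 9.2% | 75.7% |
| 0.10 | 24% | 15.6% | 64.8% |
| 0.20 | 48% | 35.2% | 40.0% |

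The rows are net of any cancellation: a PRE shift of 0.10 with half persisting at ON belongs in the 0.05 row, and with all persisting in the zero row. (Section 9.2 states 81% power where this formula gives 84.4%. That is a separate matter and does not affect the ordering.)

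**The case against.** Several objections have force.

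- **Disclosure is inferred.** No section says the participant learns the arm before the scan. Section 6.3 keeps the codes with an off-site statistician and releases one participant at a time. This stands: the point is that the plan permits early disclosure. Neither the single-blind label in Section 4.1 nor the unblinding text in Section 6.3 says participants are unaware of the arm at Scan 1.
- **Later disclosure need not reduce total expectancy bias.** If knowing the arm produces a stable difference, disclosure before PRE lets it cancel, while disclosure after PRE leaves e(ON) in the interaction. This is correct when the target is the drug effect alone. But expectancy at ON cannot be avoided in an open-label trial, and nothing in the plan supports relying on exact cancellation.
- **Section 2 makes a narrower argument.** It contrasts long-acting with daily formulations and says the two extended-release products remove a motivational imbalance. It makes an effect of expectation plausible, mainly for the cue task, but does not say that learning the allocation shifts a pre-treatment scan.
- **Day -14 looks nominal.** It heads a combined window, and Section 3.1 allows up to 30 days for screening and baseline. This stands, but it does not place randomisation after the scan.

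A reader might also infer from the Day -14 label that everyone who fails detoxification has already been randomised, and from the 75% in Section 5.3 that about 50 of 200 randomised people would be lost. The documents do not support this. Under Section 6.1, people who do not reach abstinence are not randomised. Section 5.3 pairs its 75% with a total of 160, which implies 40 lost, whereas 75% of 200 is 150. The percentage also refers to reaching the first monthly injection, so it includes losses during induction that later randomisation would not prevent.

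**Conclusion.** The point holds as a gap in sequencing. The schedule places randomisation before the baseline scan, the text does not contradict it, and no section withholds the arm until the scan is done. In a trial called open label, this leaves an avoidable route for bias into the PRE half of the primary contrast. It also leaves a period in which people can leave, knowing their arm, before they count in the all-treated population.

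Contamination is a risk and has not been shown. Its size and direction cannot be found from the documents. The percentages and error rates in the table rest on assumed net shifts and should not be read as estimates. No figure for participants lost can be supported. This is a worthwhile, low-cost improvement to the plan; it does not show that the primary comparison is invalid.

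**What to change.** Reconcile both paragraphs of Section 6.1, Section 6.3 and the schedule in Section 13.1.

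- State that allocation is generated, or at least disclosed to participants and scan staff, only after abstinence is confirmed and Scan 1 is completed, just before induction.
- Move randomisation out of the Day -14 column.
- Record the date and time of the scan and of the allocation, so the order can be verified.
- State who is blinded to what, and until when, so that Sections 3.1, 4.1, 4.2 and 6.3 agree.

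The condition should be a completed scan, not a usable one. Motion is examined during image processing (Section 8), and waiting for that would conflict with induction starting immediately after the scan.

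Sample size and number of visits are unchanged. The cost is operational: the induction drug for either arm must be ready at short notice. If that is impractical, the pharmacy can hold an allocation that is concealed from participants and scan staff until the scan ends. Losses during induction will still fall after randomisation.
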